5.0 Statistical Analysis

5.1 Analysis Plan

Data will first be assessed for outliers (+/- 2 SD from the mean) and normality. Outliers will be corrected, if possible, or dropped from the analyses. Distribution, measures of central tendency, variability, and normality will be examined. Data transformations or non-parametric techniques will be applied as needed. We will delete observations with missing values. Spearman correlation coefficients will be computed to examine associations between nerve block drug treatments, replacement surgery

type (hip versus knee), and the outcome measures (SF-MPQ, SF-8, SF- 36, WOMAC, FIM, repeated chair stand test, Opioid Symptom Distress Scale, Defense and Veterans Pain Rating Scale and its Supplemental Questions) from all time points (1 day, 2 day, 3 day, 4 day, Follow-Up Visit 1, Follow-Up Visit 2). Associations between the outcomes across time points will also be examined with Pearson (SF-MPQ, SF-8, SF-36, WOMAC, repeated chair stand test, Opioid Symptom Distress Scale) and Spearman (FIM, Defense and Veterans Pain Rating Scale and its Supplemental Questions) correlation coefficients. We will test all hypotheses and aims by conducting longitudinal multi-level modeling. The level-one unit will be the repeated measures across time, the level-two unit will be the individual patient, and the level-three unit will be nerve block type and surgical site (knee versus hip) groupings (with additional analyses involving age and diabetes status, reflecting the randomization strata). This mixed model procedure will allow the assessment of outcome and exposure variables relationships while adjusting for covariates, and separate assessments of fixed and random effects (i.e., group and individual-level data) using highly correlated repeated measures data. Covariates included in modeling will be age, diabetes status, gender, weight, smoking status, initial health status (e.g., baseline SF-8 / SF-36 and WOMAC), and concurrent general health status (e.g., daily SF-8, subsequent SF-36, and WOMAC).

The **primary hypothesis** of an improvement in pain (measured by the SF-MPQ- version 2) 24 hr after surgery during in-hospital recovery comparing plain local anesthetics versus ISOC MMPNA will be tested using a mixed model. This procedure will test for nerve block drug treatment and surgical site (hip versus knee) effects, as well as an interaction between them. Differences in pain levels will also be examined across the study's day-of surgery, 1, 2, 3, and 4 day, and Follow-Up Visit 1 and Follow-Up Visit 2 time points. The secondary aims of short- and long-term physical therapy and rehabilitation-related benefits will also be examined for nerve block drug treatment and surgical site by a mixed model. The tertiary aim to determine differences in opioid-related side effects will use a mixed model. As with other analyses, there will be an examination for nerve block drug treatment and surgical site effects, as well as an interaction between them, along with analyses of the other randomization strata (age, diabetes) as described above.

The **exploratory aims** of physical therapy progress, return-to-home benefits, etc. will be examined using a mixed model. This procedure will test for nerve block type and surgical site effects, as well as an interaction between them. Number of days from the joint replacement procedure to the patient's home discharge will be assessed. Pain responses, as measured by the SF-MPQ – version 2, and use of postoperative opioids with additional measurement by the Opioid-Related Symptom Distress Scale will also be assessed. General health status will be evaluated with the SF-8 and SF-36. Measures of pain, analgesic side-effects, and general health status will be covariates included in the modeling of the effect of MMPNA on return-to-home.

Only after all data are analyzed and results are checked and verified by the biostatisticians will the study be unblinded.

5.2 Adverse Events. For adverse events, we will calculate cumulative probability using survival analysis techniques such as the product-limit estimator. Unlike proportions, product-limit estimators can be applied at various times following randomization, and can take into account when adverse events occur. The six-week incidence (and 95% CI) of individual adverse events by organ system and relatedness to the study will be calculated for each group. We will estimate the incidence of adverse

events in both groups with specific focus on those deemed definitely, probably, or possibly related to interventions. For adverse events, clinical judgments will be considered more important than statistical testing.

Prolonged analgesic duration Sustained / prolonged nerve block analgesia, which we hypothesize to be true in our ISOC MMPNA Group, is NOT a complication that warrants medical attention as a possible complication. That this is NOT a complication is especially true in the context of perineural analgesia being designed to facilitate postoperative physical therapy in the first few days after surgery. In our evaluation of analgesic duration, a central question for patients will be “when did you first take a prescription opioid pain pill, but it did not help?” Another (indicating even further pain severity) is “when did you first get an intravenous opioid dose, but it did not help? The dates and times of these events are important and clinically practical indicators that the perineural analgesia is no longer effective. This is because postoperative oral multimodal analgesia is designed to (i) supplement the lingering analgesic effects of the nerve block, and (ii) delay the onset of the peak pain score encountered after the perineural analgesia “wears off.” “Peak rebound pain scores” may not necessarily entail excruciating pain. But if excruciating pain is encountered despite oral and intravenous opioids, then it is likely that there is no persisting perineural analgesia. Conceptually, when combining CBD with bupivacaine (in the ISOC MMPNA group), the bupivacaine provides short-lived numbness and analgesia (e.g., a theoretical 12-16 hr), but the CBD likely sustains perineural analgesia without numbness (e.g., for an additional theoretical 24 hr). The study is designed to accurately capture these two separate phases of analgesia, since we do not have preliminary data on these separate phenomena (analgesia with numbness, then analgesia without numbness).

Prolonged numbness in the distribution of the nerve blocks If a patient encounters numbness and weakness for an extended period of time after a nerve block is given, then certainly serious consideration is given to the possibility of nerve damage from surgery, nerve block, other factors, or a combination of these. We do not have any preliminary data indicating the duration of numbness as a separate entity from the duration of analgesia. In our preliminary data (published), the analgesic duration (with or without numbness) upper bound of the 95% confidence interval is 49 hr. By definition, the 95% interval (30-49 hr) is the interval representing that we are confident that the mean lies within this interval 95% of the time. So with the conservative 48 or 49 hr “upper bound” as the possible mean, and with a standard deviation of analgesic duration being 14 hr, we will apply a “mean and standard deviation” principle of “nerve damage” possibility. If the mean is 48 hr, and the standard deviation is 14 hr, then 97.5% of these nerve blocks’ numbness will dissipate by 76 hr (i.e., mean plus 2 standard deviations). For simplicity, if any patient has numbness (i.e., both analgesia and numbness, but not analgesia without numbness), beyond 72-76 hr after injection, then the participant will be referred (presumably while still in the hospital) to the Physical Medicine and Rehabilitation Service for initial evaluation, with subsequent referral to neurosurgery if deemed appropriate based on electromyography (EMG), imaging, or other workup. If minor symptoms of paresthesiae with pain and/or weakness persist over time, patients will be similarly referred to the Physical Medicine and Rehabilitation Service for outpatient workup, and these events will be recorded in study logs.

ISOC MMPNA Nerve Blocks From July 1, 2011 until December 31, 2014, there were a total of 1830 patient-block encounters involving our ISOC MMPNA program, entailing the routine use of 3-4 drugs in peripheral nerve blocks. At our institution, the incidence of EMG-documented nerve damage

attributable to the precise needle location of the block was 2/1830 (0.11%), and attributable to the precise or approximate needle location of the block was 4/1830 (0.22%). Additionally, there were 2 cases (0.11%) of postoperative EMG findings that could neither rule out nor confirm nerve damage attributable to the needle location of the block. There were also 6 cases of postoperative EMGs performed where the original suspicion of block-related nerve damage was indeed negative per EMG. Therefore, of 12 EMGs ordered, 6-8 were unable to localize nerve damage to the needle injection site. There were, separately reviewed, 7 cases of abnormal postoperative physical exam findings that were judged to be “possibly block related,” for which there was no EMG ordered to appropriately evaluate. Based on the proportions described above, we will assume that if these 7 had EMGs ordered, 3 may have proven to be positive. Therefore, in our conservative estimation, the risk of nerve damage that has been (or may be) traceable to the site of nerve block injection is 9/1830, or 0.5%. The 95% confidence interval of this incidence is 0.24% to 0.97%. In literature review, the risk of nerve damage from hip replacement ranges from 0.2% to 8% (Zappe 2014, Arch Orthop Trauma Surg 134:1477-1482). Our 95% confidence interval of the incidence of EMG-documented nerve damage (0.24% - 0.97%) lies precisely at the low end of this range. Meanwhile, contemporary estimates of risk of peripheral nerve block (PNB) anesthesia have been cited as follows. For common PNB techniques entailing the use of plain local anesthetics, the rate of neuropathy after interscalene brachial plexus block, axillary brachial plexus block, and femoral nerve block is reported as 2.84% (95% CI 1.33-5.98%), 1.48% (95% CI: 0.52-4.11%), and 0.34% (95% CI: 0.04-2.81%), respectively, based on detailed review of prospective randomized studies-to-date (as of 2007; n=10,309; Brull 2007, Anesth Analg 104:965-974). In another single-institution study of 1010 consecutive peripheral nerve blocks with plain local anesthetics, new, all-cause, neurological symptoms were present in 56/690 blocks (8.2%; 95% CI: 6.8-10.2%) at day 10, 37/1010 (3.7%; 95% CI: 2.7-5.0%) at 1 month, and 6/1010 (0.6%; 95% CI: 0.27-1.3%) at 6 months (Fredrickson 2009, Anaesthesia 64:836-844). Most symptoms (Fredrickson study) were due to causes unrelated to the block: 4 of 1010 were ultimately unrelated to the block, but for the other 2:1010 (0.2%), attribution to the block could not be ruled out. Based on the literature review described above, our 95% CI of 0.24%-0.97% for long-term complications (traced by EMG to the nerve block injection site) associated with our ISOC MMPNA (the 4-drug single-injection nerve blocks) falls within the 95% CI of published studies (lower bound of the 95% confidence interval being as low as 0.04%, and upper bound of the 95% confidence interval being as high as 5.98%) for nerve blocks using solely local anesthetics without other perineural adjuvants. We have no evidence to indicate that our ISOC MMPNA use is unsafe in the context of standard rates of complications when using plain local anesthetics, or in the context of undergoing surgery.

5.3 Incidental Findings.

All instances of incidental findings considered to be clinically significant will be addressed in the following manner: the PI will determine whether a finding is significant to warrant further action. If the PI determines the finding is serious enough to be labeled an adverse event; then the issue will be addressed with the patient’s primary care physician or another specialist. If the finding is not a serious event, then it will be listed as ‘incidental’ and no further action will be taken.

NOTE: The study team will capture the study data using CRFs that have been created by the study team. All hard copy documents will be protected and stored using generally-accepted measures for research confidentiality.

5.4 Interim Analysis.

During the course of a clinical trial, there is an ethical mandate to monitor the progress of the trial with interim analyses to ensure patient safety. A number of group sequential methods have been developed which permit comparisons to be made, while maintaining an overall type I error rate. The investigators will work with the Data and Safety Monitoring Board to select an interim monitoring approach. It is likely that an approach which adjusts the type I error rate in a non-uniform fashion, so that the majority of the type I error is conserved for the final treatment comparison. Thus, a large difference would be needed early in the trial to find a significant difference. Statistical significance parameters will be appropriately adjusted to account for these multiple interim analyses. At this time, the interim analyses are projected to occur (separately for TKA and for THA) at 5/20 patients and at 10/40 patients. If at these points the specific aims have been met (for the ISOC MMPNA treatment), then the Data Safety Monitoring Board will be charged with the decision to terminate the study.

5.5 Dissemination of Results.

The whole research team will engage in the interpretation of the study results. VAPHS will be able to disseminate the research results through email newsletters to their providers. The team will be able to present the research findings at regional provider meetings and major professional conferences including: American Society of Anesthesiologists, American Society of Regional Anesthesia and Pain Medicine, American Academy of Orthopedic Surgeons, American Physical Therapy Association, and American College of Rheumatology. The findings will be published in peer reviewed journals with appropriate access to the end user.

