ISOC MMPNA Block Group (n=80 TKA and 80 THA patients) will receive the ISOC 4-drug MMPNA nerve blocks at the L2-L4 and L4-S3 nerves/plexi. These blocks will be placed before the administration of spinal anesthesia, per our ISOC.

Active Control Block Group (n=20 TKA and 20 THA patients) will receive “active control” nerve blocks comprised of plain bupivacaine. As with the ISOC MMPNA Block Group, these blocks will be placed before the administration of spinal anesthesia, per our ISOC. Again, these blocks will involve the same L2-L4 and L4-S3 nerves/plexi as those for the ISOC MMPNA Block Group.

All study team members will be blinded to the nerve block treatment group/drug the patient receives/received for the described blocks. The only unblinded person regarding the study treatment will be the anesthesia team member who prepares the nerve block injection syringes, based on the randomization envelope assignment. This person who prepares the drug syringes will be otherwise uninvolved with the care of the study patient.

Table 1. Anatomic location of the analgesic nerve blocks used based on TKA versus THA

Basic description of regional anesthesia and analgesia care plan	TKA block details	THA details
Spinal anesthesia, L2-L4 and L4-S3 perineural/plexus single-injection nerve blocks	L2-L4 nerve block entails the femoral nerve in the groin. The L4-S3 nerve block entails the sciatic nerve as it emerges from the sciatic notch deep to the gluteal musculature.	L2-L4 plexus block entails the lumbar plexus within the psoas compartment, 2-3 inches lateral to the lumbar spine midline. The L4-S3 plexus block entails the lumbosacral trunk and parasacral plexus, which lies lateral to the lateral margin of the proximal sacrum. The plexus lies deep to the sacroiliac ligament.

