Data collection forms have been designed as paper documents (in Microsoft Word) to allow the full research team to collaborate on content; these paper documents are also being submitted to regulatory (IRB, FDA) and sponsoring (DoD) entities. If modifications to the data collection forms are required, StatCore will maintain versioning control (for both paper versions and the REDCap versions) so that new form versions will be released with prior announcement, a clear and dated history of changes will be maintained, and the final dataset will contain compatible data for analysis.

Across all data collection forms, point-of-entry data checks will be developed to ensure complete and accurate data, ensuring appropriate data precision, guarding against missing or out-of-range data, and prompting for correction of illogical data (e.g. post-surgical procedures dated prior to surgery date). Branching logic will be used as is feasible to ensure that only relevant questions are presented (e.g. if the question “Ever smoked cigarettes?” is answered “No”, subsequent questions about smoking history are skipped). The system maintains a full audit trail, identifying each change to the entered data both by date/time and person, and recording both prior and current values, to ensure recovery of inadvertently changed data. It also provides user roles that define read, write, change, and delete privileges on an individual data collection form basis.

Documentation

Working with the study PIs and coordinators, the Clinical Trial Center and StatCore will finalize a Manual of Operating Procedures (MOP, currently in draft phase) to standardize all procedures and staff training in areas such as patient recruitment, measurement, and assessment, as well as data entry, management, and security.

A comprehensive data dictionary and code book has been created during study startup, and will be maintained throughout the study, logging any data field changes or coding changes. This dictionary will identify and characterize all fields available for analysis, and will provide a useful reference document for continuing analysis of the study data. We anticipate that the final versions of the MOP and data dictionary will be available for regulatory or related reviews approximately 12-15 months after study inception.

Confidentiality and Identifiers

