5.6 Sample Size Determination

Although the SF-MPQ data is the basis of our specific aim, we do not have our own preliminary SF-MPQ data. So we will base our sample size on our most robust data, that being nerve block duration from our observational data (40 hr mean, with 14 hr standard deviation). Hip replacement and knee replacement surgery are different procedures requiring anatomically different nerve blocks as described above, so we will consider these samples as separate. We consider a doubling of the nerve block duration (15 hr for plain bupivacaine, 30 hr for bupivacaine-CBD) as a clinically significant difference with respect to the military objectives of evacuation and transport. We forecast that as a single-drug (and based on historical literature), the standard deviation of plain bupivacaine duration would be half of the 15 hr projected duration (i.e., 7.5 hr). Due to likely variability in study participant responsiveness to the 4-drug mixture, we predict that the standard deviation of the bupivacaine-CBD treatment would also be half of the projected 30 hr duration (i.e., 15 hr). We believe that the 30 (SD=15) hr duration for bupivacaine-CBD is a reasonably conservative duration based on our preliminary data of 40 (14) hr block duration. Using a 2-tailed t-test with $\alpha=0.05$, 20 patients per procedure for bupivacaine treatment, and 80 patients per bupivacaine-CBD treatment would yield 95% statistical power. This sample size will also accommodate for our multiple secondary aims. Attrition of 6 active control treatment patients ($n=14$) and of 24 MMPNA-treated patients ($n=56$) will still yield just over 80% statistical power. All calculations were performed using IBM SPSS SamplePower version 3.0.1, Chicago, IL.

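### Section 5.1 drops genuine values beyond ±2 SD, including on the primary outcome: a pooled cut shrinks the treatment difference, and a per-arm cut raises type I error to about 8–11%

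*Combined protocol and SAP*

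**What the plan says.** Section 5.1 (Analysis Plan) opens with "Data will first be assessed for outliers (+/- 2 SD from the mean) and normality" and continues "Outliers will be corrected, if possible, or dropped from the analyses". It then adds "Data transformations or non-parametric techniques will be applied as needed". The rule covers data in general. It does not exempt the primary 24-hour SF-MPQ, does not require evidence of a recording error before a value is dropped, and does not say whether the mean and SD are pooled, per arm, per procedure or per visit. No analysis with all values retained is planned.

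Three other places bear on the point:
- Section 4.4 (Data Collection) already plans point-of-entry checks, "guarding against missing or out-of-range data, and prompting for correction of illogical data".
- Section 5.1 later states "Only after all data are analyzed and results are checked and verified by the biostatisticians will the study be unblinded".
- Section 4.1 allocates 4:1. The smaller arm is "Active Control Block Group (n=20 TKA and 20 THA patients"), against 80 and 80 in the MMPNA arm. For sample size, section 5.6 treats hip and knee as different procedures, "so we will consider these samples as separate".

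**The concern.** Two SD is not an error threshold, because a fixed share of perfectly valid data lies beyond it. Many recording errors should already have been caught at entry, so what this step meets will be largely genuine. Such a value cannot be corrected, and the only outcome left is deletion.

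The documents themselves suggest where the extremes will fall. Section 2.1 gives plain bupivacaine blocks 8–16 hours and the 4-drug block about 36 hours. At 24 hours, many control blocks should have worn off while most MMPNA blocks still work. High control scores at that time are the treatment signal. With four MMPNA patients to each control patient, a pooled mean and SD describe mainly the MMPNA arm, so high control scores are the ones most likely to be cut.

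A per-arm cut does a different harm. The difference stays unbiased for symmetric data, but the residual SD is too small, so the test rejects too often. Because the cut is not defined, a reader cannot tell which harm applies.

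**Working it through.** **The plan's own figures.** The plan gives no figure for the effect of this rule. Its power figures (section 5.6) concern block duration and cannot serve as an SF-MPQ benchmark: the sponsor states "we do not have our own preliminary SF-MPQ data". The SF-MPQ effect sizes and shapes below are therefore assumptions, shown as a range.

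**Share removed.** For normal data P(|Z| > 2) = 4.55%, and 0.0455 × 200 = 9.1 values per time point (4–5 of 100 within one procedure). Simulated shares are 4.0–5.3% for normal, gamma, exponential, lognormal, t(5) and zero-inflated shapes, but 1.6–4.0% for bounded beta shapes and about 0–0.2% for uniform data. Over four post-operative days, 10–14% of patients lose at least one value.

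**Pooled cut, by hand.** Take control N(0.5, 1), MMPNA N(0, 1), weights 0.2 and 0.8.
- Pooled mean = 0.2 × 0.5 = 0.10. Pooled variance = 1 + 0.2 × 0.8 × 0.5² = 1.04, so SD = 1.020.
- Cut points = 0.10 ± 2.040, that is −1.940 and 2.140.
- Control, in its own SD units: −2.440 to 1.640. Dropped: 5.8%.
- MMPNA: −1.940 to 2.140. Dropped: 4.2%.
- Mean after truncation = μ + [φ(a) − φ(b)] / kept share.
- Control: 0.5 + (0.0203 − 0.1040)/0.942 = 0.411.
- MMPNA: 0 + (0.0608 − 0.0404)/0.958 = 0.021.
- Difference = 0.411 − 0.021 = 0.39 instead of 0.50, or 22% too small.

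Simulated t-tests at 40 vs 160 agree: estimate 0.39, power 80% to 68%.

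**Per-arm cut.** Truncating N(0, 1) at ±2 gives SD = √(1 − 4φ(2)/0.9545) = 0.88. The standard error uses this reduced SD, although the difference in means does not become correspondingly more precise. Simulated type I error for a t-test at 40 vs 160 is 9.8% (normal) or 11.3% (gamma, shape 1.5).

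**Closer to the planned analysis.** This is a random-intercept REML model with day effects over four post-operative days, one pass of the cut at each day, and within-patient correlation 0.5–0.8.

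| Scenario | Estimate with pooled cut | Power, all data → pooled cut |
|---|---|---|
| 40 vs 160, true 0.50 SD | 0.42–0.43 | 80% → 73–74% |
| Same, effect fading after day 1 | 0.42–0.45 | 80–81% → 74–78% |
| 20 vs 80, true 0.70 SD | 0.59–0.60 | 79% → 72% |

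| Null rejection rate | All data | Pooled cut | Per-arm cut |
|---|---|---|---|
| 24-hr contrast, 40 vs 160 | 4.9% | 4.4–5.2% | 8.4–8.7% |
| Treatment main effect, 40 vs 160 | 5.1–5.7% | 5.6–5.8% | 8.4–11.0% |
| 24-hr contrast, 20 vs 80 | 4.3–4.7% | 4.9% | 8.1–9.2% |

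The patient's other days reduce the pooled bias but do not remove it, because values removed for their own size are not missing at random.

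**Spread across other assumptions** (single-time-point t-test, 40 vs 160, pooled cut):
- Gamma, shape 1.5, control mean × 1.5: 50% shrinkage, power 82% to 50%.
- Same gamma, pure 0.5 SD shift: 13% shrinkage, but power rises from 81% to 89%.
- Section 5.6 block-duration inputs (15 vs 30 hr, SD 7.5 and 15): pooled mean 27, SD √(0.2 × 56.25 + 0.8 × 225 + 0.16 × 225) = 15.07, cuts at −3.15 and 57.15. The difference falls from 15 to 14.16 hr (5.6%), with no loss of power.

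**The case against.** The strongest reply has four parts.

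- **The type I inflation needs the less natural reading.** The text speaks of one mean, and unblinding follows verification of the results, which points to a pooled cut with error near 5%. This stands as a limit on that figure. It does not rule out a per-arm cut: fitting the model needs arm codes, and coded arms can be trimmed separately. The 11% upper end comes from a four-day main effect or a single-time-point t-test on skewed data, not from the 24-hour mixed-model contrast.
- **Transformation may rescue skewed data.** The order of trimming and transforming is not stated. If the gamma data are log-transformed before a pooled cut, shrinkage is 16% with almost no power loss (66% to 65%); with a square root it is 35% (78% to 53%). The remedy is partial, is offered only as needed, and is not said to replace dropping. A rank test after a per-arm cut at 20 vs 80 still rejects 7.6–8.4% of the time under the null.
- **The sizes are assumed, and some cases are mild.** True, as the block-duration and pure-shift cases show.
- **Bias toward no difference is conservative for a superiority claim.** That protects against a false positive, but the estimate is still wrong and power is usually lost.

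Nothing elsewhere in the document limits the rule.

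**Conclusion.** The concern holds. As written, the plan deletes genuine values of the primary outcome because of their size, against an undefined reference mean. That part rests on no distributional assumption. About 4–5% of values go if the data are roughly normal or skewed, and fewer for some bounded shapes.

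Under a pooled cut, the best available approximation to the planned model gives a difference 10–17% too small and a loss of about 2–7 percentage points of power at a true 0.50 SD. Single-time-point analyses range from 5.6% to 50% shrinkage. Under a per-arm cut, the nominal 5% error becomes about 8–11%. The simulations omit the planned covariates, the surgical-site interaction and the third model level, and the SF-MPQ effect, SD and shape are assumed. The direction of the pooled bias, toward no difference, was the same in every scenario tested; its effect on power was not. Because the rule acts directly on the primary test, it should be changed before the analysis.

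**What to change.** Replace the outlier sentence in section 5.1 with wording such as:

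> All recorded values are analysed in the primary analysis. A value is changed or set to missing only when source documents show a recording error, and that decision is made before unblinding. No value is excluded for its size.

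The ±2 SD flag can stay as a trigger for a source-document check. Any outlier-excluded, robust or rank-based result should be a pre-specified sensitivity analysis that states whether the cut is pooled or per arm and that it is applied at each time point.

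The cost is one SAP sentence, with no extra data or patients. The residual SD will be somewhat larger than after trimming (the trimmed SD is about 0.88 of the true SD in normal data). With skewed scores and a pure shift, the all-data t-test had less power than the trimmed one (81% against 89%); the rank-based sensitivity analysis can address that case.
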